6.3.2 Secondary outcome(s)

- SO1. Baseline clinical and sociodemographic characteristics of children will be summarized using descriptive statistics;

Secondary criteria related to the performance and the clinical benefit of Petit Drill will be described as follow:

- SO2. Score global and score of the 5 items of PCQ (Q1: cough frequency, Q2: sleep disturbance of the child, Q3: sleep disturbance of the parent, Q4: cough severity, Q5: degree of bothersomeness to the child) will be described after 1, 2 and 3 day-treatment with Petit Drill. The percentage of children with a 3 point-decrease of PCQ total score from baseline at 1 and 2 day-treatment with Petit Drill will be described;
- SO3. Daily cough severity will be measured using visual analogue scale (VAS) ranging from 0 (no cough) to 100 (worst cough) in response to "Yesterday, how was the cough of

my child during the day?", measured VAS after 1, 2 and 3 day-treatment with Petit Drill. the evolution of scores from baseline will be described;

•SO4. Scores of the Parent-proxy Children's Acute Cough-Specific Questionnaire PAC-QoL (global and dimensions) will be collected at baseline (D1) and after 3 day-treatment with Petit Drill (morning D4), or on the next morning of the last day of treatment. The evolution of scores from baseline will be described.

Secondary criteria related to the assessment of use and the safety of Petit Drill will be described as follow:

- SO5. The mean (SD) number of times Petit Drill was administered in each 24-hour period from the first (D1) to the third (D3) day of treatment initiation will be described;
- SO6. Parent's satisfaction with Petit Drill use will be described using a questionnaire, and responses measured using Likert scales. Responses will be presented as percentages;
- SO7. Safety will be assessed by the analysis of:
 - Adverse events (frequency, severity, emergence, and causal relationship of adverse events) tabulated according to IMDRF terms (International Medical Device Regulators Forum, Annex E). Number and percentage of relevant AEs during treatment with Petit Drill, defined as all SAEs or AEs related to the device, and any AEs of special interest;
 - Number and percentage of device deficiencies.

6.3.3 *Exploratory outcomes*

- SO8. The percentage of children receiving Petit Drill with or without physician prescription will be described by two age groups: from 6 months to 12 months old and from 13 months old to 6 years of age;
- SO9. To assess all outcomes, except SO8, in the subgroup of children aged 6-24 months and subgroup of children aged 25 months to 6 years.

PRO questionnaires in order to assess the user's perspective of the device's performance are given below. The variables for each questionnaire are detailed in section 6.4.

The Pediatric Cough Questionnaire (PCQ) (Annex III)

The PCQ is a reliable and validated questionnaire by Hartnick *et al.* [17]. The five questions, which could be answered by the child's parent or proxy, cover cough frequency (Q1), sleep disturbance of the child (Q2), sleep disturbance of the parent (Q3), cough severity (Q4), and the degree of bothersomeness to the child (Q5). Each of the five items was scored on a 6-point Likert scale, from 0 to 5, and possible over scores range from 0 to 25. The higher the scores, the higher the severity. A 3-point difference in PCQ score is clinically significant.

Parent-proxy Children's Acute Cough-Specific Questionnaire (PAC-QoL) (Annex IV)

The PAC-QoL instrument is an acute cough-specific QoL in young children, that measures the burden, of acute cough in children. Original PAC-QoL₁₆ has been validated by Anderson-James *et al.* [18], then re-validated by Anderson-James *et al.* [19] concomitantly with the shorter form of 6 items (PAC-QoL₆), that has been found as robust and as reliable than the 16 item-form.

PAC-QoL₆ consisted of 6 items utilizing a 7-point Likert-type rating scale (1 = all the time or very, very worried and concerned to 7 = none of the time or not worried and concerned). Items referred to a 24-hour recall. Higher PAC-QoL scores reflect better QoL with lower scores reflecting greater frequency

and worries or concerns. The minimal clinical significance for the overall PAC-QoL₆ questionnaire is therefore estimated to be 0.71–1.11 [19].

Daily cough severity using an electronic VAS (Annex V)

Subjective assessment of cough severity using 0-100 VAS for rating cough severity (0: no cough to 100: worst cough) has been validated by Lee *et al.* [20]. In this clinical investigation, subjective assessment of cough severity will be performed using e-VAS thanks to NursTrial® App. Even length of the scale could vary depending on the screen of the patient' smartphone, electronic and paper VAS presented comparable results, as 100 mm length is not a requirement [21].

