For secondary safety outcome: number and percentage of AEs, including device deficiencies (DD) (to be completed by the investigator during an interview with the parent/legal representative)	Once a day, at a time of choice and at investigation end.	All AEs during the 3-day period will be asked to be reported by the patient, whether they think it is related to the investigational device or not. Once a day the following questions will be asked. 
• Today did your child experience any sort of illness or negative effects (whether related to the Syrup or not)? Yes/ No If yes, please contact the investigator.
		CONFIDENTIAL V6.0 #Sans suivi modifications#26-MAR-2024 Page 34/65

Pierre Fabre

CLINICAL INVESTIGATION PLAN (CIP)

Outcome	Suggested schedule	Variables
Adherence	At least once a day or at each intake	
How many times in the previous 24 hours did your child use Petit Drill? (Insert a single digit number)
 
For each dose, please give the approximate time: HH:MM
 
If Petit Drill is stopped before the recommended treatment duration of 3 days, please specify the reason:
 
Cough improvement / Cough worsening / Other /Other specify

Parent Satisfaction with Petit Drill Syrup Use	At study end (after 3 days of use)	
 How would you rate the quality of therapeutic management your child received? (Excellent/ Good/ Fair/ Poor) To what extent did this treatment meet your child's needs? (Almost all of my child's needs were met/ Most of my child's needs were met/ Only few of my child's needs were met/ None of my child's needs were met) Would you recommend this treatment to another parent? (No, definitely not/ Not really/ Yes, generally/ Yes, definitely) How satisfied are you with information received from the IFU to use this treatment? (Quite dissatisfied/ Indifferent or mildly dissatisfied/ Mostly satisfied/ Very satisfied) In a general sense, was it easy to use this treatment? (No, definitely not/ Not really/ Yes, generally/ Yes, definitely) Did your child seem to like the taste of the syrup? (No, definitely not/ Not really/ Yes, generally/ Yes, definitely)

Pierre Fabre

CLINICAL INVESTIGATION PLAN (CIP)

Table 4: Variables to be collected by the investigator in case of AE or DD occurring during patient follow-up

Outcome	Suggested schedule	Variables

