6.9.5 Expected duration of each subject's participation

Subjects will be followed-up for 3 days since the initiation of the Petit Drill® syrup intervention.

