The patient's follow-up will last as long as he/she receives Petit Drill but will not exceed 3 days and 3 nights. Indeed, to stay close to real-word condition of use of Petit Drill, the treatment duration is recommended as per IFU but not imposed in the present clinical investigation. However, the parent must specify reason for stopping the treatment in the App.

During the follow-up, the patient's parent will have to complete the daily questionnaire and record Petit Drill intake in the App. Parents will be asked to inform the investigator of any adverse event as soon as possible.

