14 MANAGEMENT AND REPORTING OF ADVERSE EVENTS, ADVERSE DEVICE EFFECTS AND DEVICE DEFICIENCIES

14.1 Definitions

A qualified and suitably trained medical professional will assess all declared adverse events (AE) and adverse device effects (ADE), that would be reported by the patient/parents during the 3 days of using Petit Drill.

All definitions are issued from REGULATION (EU) 2017/745 OF THE EUROPEAN PARLIAMENT AND OF THE COUNCIL of 5 April 2017 on medical devices, and corresponding Medical Device Coordination Group (MDCG) guidelines.

14.1.1 *Adverse Event (AE) - Article 2 (57) from MDR*

Any untoward medical occurrence, unintended disease or injury or any untoward clinical signs including an abnormal laboratory finding, in subjects, users or other persons, in the context of a clinical investigation, whether or not related to the investigational device.

Note 1: This includes events related to the study product (including test product and/or associated products) and/or related to the procedures involved (any procedure in the clinical investigation plan).

Note 2: For users or other persons this is restricted to events related to the investigational medical device.

Note 3: An Adverse Device Effect (ADE) is an AE related to the use of the investigational medical device.

14.1.2 *Serious Adverse Events (SAE) - Article 2 (58) from MDR*

Any adverse event that led to any of the following:

- (a) death,
- (b) serious deterioration in the health of the subject that resulted in any of the following:
 - (i) life-threatening illness or injury,
 - (ii) permanent impairment of a body structure or a body function,
 - (iii) hospitalisation or prolongation of patient hospitalisation,
 - (iv) medical or surgical intervention to prevent life-threatening illness or injury or permanent impairment to a body structure or a body function,
 - (v) chronic disease.
- (c) foetal distress, foetal death or a congenital physical or mental impairment or birth defect.

Note 1: A planned hospitalisation for pre-existing condition, or a procedure required by the protocol, without a serious deterioration in health, is not considered to be a serious adverse event.

Note 2: This also includes device deficiencies that might have led to a SAE if a) suitable action had not been taken or b) intervention had not been made or c) if circumstances had been less fortunate.

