14.3 Reporting of medical device cases

All AEs and DD that would occur during the 3-day follow-up period will be asked to be reported by the parents/guardians via the mobile application daily, whether they think it is related to the investigational device or not. The questionnaire to be used by the parents/guardians is provided in Table 3 above.

The questionnaire will be formulated such that the parents/guardians will be able to describe the AE to allow the determination of seriousness and causality by the investigator.

Following a declaration, an automatic notification will be sent to the investigator who will then be required to follow-up on the event.

The following would be defined as elements that could be a potential AE during the 3-day follow-up:

- Any new illness or symptom (diagnosed or undiagnosed);
- Any worsening of an existing illness or symptoms (diagnosed or undiagnosed);
- Any usual or unusual health-related event (such as loss of appetite, teething pain, reflux etc.).

Investigator's responsibility:

All these foreseeable events can be mitigated by carefully reading the IFU and by storing the device out of the reach of children and in suitable conditions as detailed in the IFU.

All AE, SAE and DD observed during the study must be reported in the eCRF by the investigator. Each AE must be assessed for seriousness, severity and causality by the investigator.

For AE or SAE including DD whether or not considered as related to the device or to the procedure the investigator will complete immediately and within 3 calendar days the form (FORM_CVI_6585) "Solicited adverse event collection form" and collect the results of the carried-out examinations and the reports of hospitalisation if applicable.

In case the investigator is aware of any new information, it should be reported to the sponsor.

Contractor's responsibility:

The contractor conducting the study will be required to provide the following information that has been brought to his attention about the investigational device within 1 business day after its acknowledgment in the eCRF:

- Any AE or SAE including DD which arises from the use of Petit Drill;
- Any SAE considered as related to the procedure of the study.

The safety information will be communicated to Pierre Fabre Vigilance department no later than 24 hours upon its reception by the contractor, through the form (FORM_CVI_6585) "Solicited adverse event collection form", which will be sent by email: [contact].

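### SO7 limits its relevant-AE percentage to the treatment period while the AE window is stated in two conflicting ways, so a serious or related event after an early stop can be left out

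*Protocol*

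**What the plan says.** SO7 has two AE components. The first is a general tabulation with no limit tied to treatment: "Adverse events (frequency, severity, emergence, and causal relationship of adverse events) tabulated according to IMDRF terms". The second is narrower: "Number and percentage of relevant AEs during treatment with Petit Drill, defined as all SAEs or AEs related to the device", together with AEs of special interest. The synopsis repeats both. The protocol does not say when the treatment period ends for this count, for example at the last dose or some time after it.

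Three days of use are not compulsory: section 6.10 states that "the treatment duration is recommended as per IFU but not imposed in the present clinical investigation". Table 3 asks for the reason for an early stop and lists cough improvement, cough worsening and other.

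The AE window is stated in different ways:
- Table 3 (section 6.4): "All AEs during the 3-day period will be asked to be reported by the patient", with a question once a day and at the end of the investigation.
- Section 14.3: "All AEs and DD that would occur during the 3-day follow-up period will be asked to be reported by the parents/guardians".
- Section 6.9.5: "Subjects will be followed-up for 3 days since the initiation of the Petit Drill® syrup intervention". Sections 6.1 and 8.1.2 also set a three-day period, the latter counted from inclusion.
- Section 14.1 treats the window as days of use: "reported by the patient/parents during the 3 days of using Petit Drill".
- The synopsis and section 6.10 (study follow-up) tie the length of follow-up to receipt of the syrup, with three days and three nights as a maximum.

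Under section 7.1 the safety population is every child with at least one use. Section 7.2 plans 95% confidence intervals for the safety outcomes.

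**The concern.** The relevant-AE percentage is the one SO7 figure that isolates serious and device-related events. Its numerator is limited to treatment, but its denominator keeps every child who took one dose. For a child who stops early, the counting window can close while the AE window of Table 3 and sections 6.9.5 and 14.3 is still open. A device-related reaction that starts the day after the last dose is still device-related, yet the literal wording need not count it.

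The study is meant to supply safety data for the clinical evaluation (sections 4.6 and 5), and section 5.3 says that such data come from a clinical investigation for the first time. Few serious or related events are likely to be seen, so a single one changes the reported percentage and its upper confidence limit visibly. Any error from the omission can only lower the figure.

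**Working it through.** **1. The plan's own figure.** Section 7.4 gives 196 evaluable and 245 enrolled children. With half-width 7% at p = 50%: n = 1.96² × 0.5 × 0.5 / 0.07² = 195.99, so 196; then 196 / (1 − 0.20) = 245. Both reproduce. The point does not depend on them, except that 245 is the planned upper bound for the safety denominator. The 196 belongs to the precision of the primary outcome and is not the safety denominator.

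**2. The windows side by side**, for a child who takes the last dose on D2 and has a serious or related event that starts on D3:

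| Place | Window | D3 event |
|---|---|---|
| Table 3; 6.1; 6.9.5; 8.1.2; 14.3 | three days from initiation or inclusion | solicited |
| Synopsis and 6.10, study follow-up | as long as the syrup is received | may not be solicited |
| 14.1 | three days, described as days of use | unclear |
| SO7, general AE tabulation | no treatment limit stated | shown if reported |
| SO7, relevant AEs | treatment period, end not defined | can be left out |
| 7.1, safety population | at least one use | child stays in denominator |

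On the fixed three-day reading, the event is collected and tabulated but can be missing from the relevant-AE number and percentage. On the treatment-linked reading, it may not be asked about. Even then contact does not end with the last dose: section 6.3.1 has the final PCQ value rate the night after the day of stopping and be collected the next morning.

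**3. Size.** The protocol gives neither an early-stopping rate nor an event rate, so no single corrected figure exists. Assume that all 245 children are treated and that the interval is exact (Clopper-Pearson). With no event, the upper limit is 1 − 0.025^(1/245) = 1.49%. With one event, the estimate is 1/245 = 0.41%, and the upper limit is the 97.5% point of a Beta(2, 244) distribution, 2.25%. Further event counts are assumed:

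| Relevant events | Percentage | 95% CI |
|---|---|---|
| 0 | 0% | 0 to 1.49% |
| 1 | 0.41% | 0.01 to 2.25% |
| 2 | 0.82% | 0.10 to 2.92% |
| 3 | 1.22% | 0.25 to 3.54% |

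**4. Time at issue.** If a fraction s stops after day d, the share of three-day child-time after stopping is s × (3 − d)/3. For assumed s from 5% to 30%, this is 1.7% to 10% when d = 2 and 3.3% to 20% when d = 1. This is a share of time and not of events.

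**The case against.** The strongest reply is that there may be no mismatch. If follow-up ends with treatment, as the synopsis and section 6.10 say, collection and counting close together. That reading is available, but it contradicts section 6.9.5 and sits badly with Table 3 and sections 8.1.2 and 14.3. It also leaves late events unsolicited, which is no better for a safety figure. The reply therefore shows that the follow-up wording has to be reconciled as well.

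Second, the end of the treatment period is undefined, and the protocol leaves the calculation of variables to the SAP, which is not at hand. The SAP could include a period after the last dose. This stands, and it is why the conclusion is that an event can be left out, not that it will be. The limit itself, however, is written into the outcome definition, and an SAP that counted to D4 regardless of stopping would depart from its literal wording.

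Two stronger readings are tempting:
- A reader might infer that post-stop serious events disappear from the safety results. The documents do not support this: the general AE tabulation has no treatment limit, and section 14.3 requires all AEs, SAEs and device deficiencies to be entered in the eCRF.
- A reader might infer that the percentage is bound to be too low because early stoppers are the children most at risk. This is not supported either. Improvement is a listed reason for stopping. An event that prompted the stop would have begun on treatment, and Table 4 records its start date, so it can be counted.

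**Conclusion.** The point holds in a limited form. SO7 restricts the relevant-AE number and percentage to an undefined treatment period, early stopping is allowed, and the protocol states two incompatible follow-up periods. A serious or device-related event that starts after an early stop and within three days can be left out of that summary while the child remains in the denominator, or may not be solicited at all. Only the relevant-AE summary and its confidence interval are affected among reported events.

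The size is unknown, because no stopping or event rate is given. With up to 245 treated children and an exact interval, one omitted event would be the difference between 0% (upper limit 1.49%) and 0.41% (upper limit 2.25%). The conclusion rests on reading the treatment period as ending at or near the last dose. The change is worth making because it costs little and removes a possible downward error from a safety percentage.

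**What to change.** State one AE observation window: from the first dose to the end of the three-day follow-up (morning of D4), whether or not the syrup was stopped. Then:
- Use it in place of the treatment limit in the SO7 relevant-AE count, in the synopsis and in section 6.3.2.
- Reconcile the follow-up wording in the synopsis and section 6.10 with sections 6.1, 6.4 (Table 3), 6.9.5, 8.1.2 and 14.3, so that AE questions do not end when the syrup does. Align the phrase in section 14.1 at the same time.
- Optionally, show on-treatment events as a sub-row.

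The cost is a few wording changes. The daily AE question continues to D4 for children who stop early, and the relevant-AE figure may be slightly less favourable. The change concerns observation and counting only and leaves the use of the syrup untouched.

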	
Pharmacist will briefly present the clinical investigation to the parent who purchases Petit Drill for his/her child from 6 months to 6 years old. A prescription will be mandatory for infant patients from 6 to 12 months old.
 
If the parent does not want to participate but gives the pharmacist his/her agreement, the pharmacist will record in a pre-screened log child's age and gender, and main reason of parent's refusal.
 
If the parent is interested, the pharmacist will provide the study information note and transfer the parent's name and contact information to the clinical investigation centre (CEN Expérimental).
 
Inclusion visit:
 
Upon receipt of a pre-screen patient, the parent will be contacted to take part to the remote inclusion visit with an Investigator (General Practitioner) of CEN Experimental, scheduled within the day of Petit Drill delivery.
 
Before proceeding with the signing of the consent, the Investigator will first ensure that the parent is duly informed. Consent will be electronically signed using a solution (DocuSign) whose functionality meets recommended expectations of the Guidance on computerized systems and electronic data in clinical trials (EMA/INS/GCP/112288/2023). In non-single-parent households, the informed parent who signed the consent will remain the one who completes the study data in the ePRO App NursTrial®.
 
If several children are eligible in the same household, an algorithm will randomly select one of them. Then, the Investigator will check the inclusion and exclusion criteria, and proceed to the patient's enrolment.
 
The Investigator will record the necessary study data in the e-CRF (socio-demographics, baseline medical data). A Clinical Research Associate will help the parent download the NursTrial® App on their smartphone and create their personal access. Then, the parent will complete the study questionnaires in the App.
 
Study follow-up:
 
The patient's follow-up will last as long as he/she receives Petit Drill but will not exceed 3 days and 3 nights.
 
During the follow-up, the patient's parent will have to complete the daily questionnaire and record Petit Drill intake in the App. Parents will be asked to inform the Investigator of any adverse event as soon as possible.

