5.1 Objectives

5.1.1 *Primary objective*

To assess the performance of the Petit Drill medical device in the treatment of throat irritation (sore throat) associated with dry cough in infants starting at 6 months of age and in children up to 6 years of age.

5.1.2 *Secondary objectives*

- SO1. To describe the clinical and sociodemographic characteristics of children using Petit Drill.

The following secondary objectives will describe the performance and clinical benefit of Petit Drill in terms of:

- SO2. Changes in nightly cough frequency, severity, bothersome for the child, and ability to sleep for child and parent(s) throughout the 3 day-treatment;
- SO3. Changes in daily cough severity;
- SO4. Evolution of Quality of life.

The following secondary objectives will describe the use and safety of Petit Drill:

- SO5. Adherence to use of Petit Drill Syrup;
- SO6. Parents' satisfaction with Petit Drill use;
- SO7. Safety of the Petit Drill medical device in infants aged from 6 months to children up to 6 years of age.

5.1.3 *Exploratory objectives*

- SO8. To describe the dispensing modalities of Petit Drill by age group;
- SO9. To describe the study objectives (except SO8) according to child's range of age.

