6.4 Variables

Variables to be collected in pre-screening log by the pharmacist:

- Patient age in years and months;
- Reason for non-inclusion to the investigation (if applicable). For example: antibiotics, previous cough treatment;
- Reason for refusal to participate in the investigation (if applicable).

Variables to be collected in screening log by the investigator:

- Patient age in years and months;
- Reason for non-inclusion to the investigation (if applicable);
- Approximate date of dry cough start;
- PCQ-score (based on the recall of the night prior inclusion) – only patients with a score of 3 or above at least for 3 of the 5 items of PCQ are to be included (see section 6.9.1).

Table 2: Variables to be collected at patient enrolment

Sociodemographic data and dispensing modalities	Age in years and months
(To be recorded by the investigator in the eCRF)	Rank among siblings
	Weight and height
	Sex and geographic region
	Did the patient receive a doctor's prescription for Petit Drill? (Yes/No)
Baseline medical data	Pre-existing medical conditions
(To be recorded by the investigator in the eCRF)	Investigator's assessment of patient's condition Acute dry cough Yes/No
	Approximate date of dry cough start
	Prior treatments for ongoing cough
	Ongoing, non-interfering medications
Associated symptoms at baseline	
	Fever (Yes/No)
	Runny nose (Yes/No)
	Congestion (Yes/No)
	Sore throat (Yes/No)
	Ear Pain (Yes/No)
	Sensation of pain or more frequent crying than usual (Yes/No)
	Digestive symptoms (vomiting or diarrhoea) (Yes/No)
	Reduced appetite (Yes/No)
PCQ (to be recorded by the parent/legal representative in the NursTrial® app with the help of the investigator)	
CONFIDENTIAL	V6.0 #Sans suivi modifications#26-MAR-2024
	Page 31/65

Q1. How frequent was your child's cough last night?	0- Not at all
	1- Occasionally
	2- A little
	3- Somewhat
	4- Very much
Q2. How much did last night's cough affect your child's ability to sleep?	5- Extremely
	0- Not at all
	1- Occasionally
	2- A little
	3- Somewhat
Q3. How much did last night's cough affect your ability to sleep?	4- Very much
	5- Extremely
	0- Not at all
	1- Occasionally
	2- A little
Q4. How severe was your child's cough last night?	3- Somewhat
	4- Very much
	5- Extremely
	0- Not at all
	1- Occasionally
Q5. How bothersome was last night's cough to your child?	2- A little
	3- Somewhat
	4- Very much
	5- Extremely
	0- Not at all

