6.9 Subjects

If the parent/legal representative does not want to participate but gives the pharmacist his/her agreement for pseudonymous data collection of his/her response, the pharmacist will record in a pre-screened log the following data in the study website:

- Patient age in years and months;
- Reason for refusal to participate in the investigation (if applicable);
- Reason for non-inclusion to the investigation (if applicable, i.e., patient not meeting a main entry criteria).

6.9.1 *Inclusion criteria*

Children meeting the following inclusion criteria will be included:

- IC1. Boys or girls, 6 months to 6 years of age;
- IC2. With one of his/her parents/legal guardian purchases Petit Drill in a participating pharmacy in accordance with recommendations for use (regarding age and type of cough);
- IC3. For infants between 6 months and 12 months of age – a confirmed prescription from a treating physician;
- IC4. With an acute cough lasting less than 48 hours
- IC5. With a score ≥ 3 at least for 3 of the 5 items of PCQ, (based on assessment of the night before inclusion);
- IC6. For whom child-minding will allow to respect the recommended daily doses* of Petit Drill during the 3 day-treatment;
- IC7. With a parent/legal guardian having a smartphone allowing using the ePRO App. NursTrial®;
- IC8. With a parent/legal guardian able to understand and to complete to the questionnaires in timely manner;
- IC9. With parent(s)/legal guardian who provide their signed informed consent for the child's enrolment in the study.

* 2-4 doses on D1, then 3 to 4 doses on D2 and D3, including one of the daily doses taken at bedtime.

6.9.2 *Exclusion criteria*

Children meeting one of the following exclusion criteria will not be included:

- EC1. Presenting with one of the following conditions:
 - Chronic respiratory illness such as asthma, recurrent wheezing associated to viral infections and bronchitis;
 - Lower respiratory infections, such as bronchitis, bronchiolitis, and pneumonia;
 - Angina, otitis, or sinusitis;
 - Persistent cough lasting more than 3 weeks, whatever the etiology;
 - Gastrointestinal pathology, involving vomiting, nausea, or diarrhoea.
- EC2. With ongoing use of paracetamol, and/or homeopathic products against cough;
- EC3. Having had corticosteroid treatment, antibiotics, antihistaminic or any cough medication (such as, but not limited to, Phytoxil, Arkotoux) in the previous 15 days since inclusion;

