8.1.3 Specification of source documents

Since Petit Drill® Syrup is an OTC medication that can be purchased from the pharmacy without a prescription, the patient will not be managed in a medicalized setting. Therefore, no source documents will be available or required. Baseline data will be recorded by Investigator of CEN Expérimental via interviews with the patients' parents and legal guardians.

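### SO8 cannot describe dispensing in infants of 6–12 months, because IC3 fixes their prescription share at 100% (exploratory outcome, minor impact)

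*Protocol*

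**What the plan says.** The objective in Protocol 5.1.3 reads "SO8. To describe the dispensing modalities of Petit Drill by age group". The matching outcome in 6.3.3, repeated in the Synopsis, is: "The percentage of children receiving Petit Drill with or without physician prescription will be described by two age groups", namely "from 6 months to 12 months old and from 13 months old to 6 years of age".

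Eligibility is set in 6.9.1 and in the Synopsis. IC3 reads: "For infants between 6 months and 12 months of age – a confirmed prescription from a treating physician". The Synopsis description of pre-screening says the same: "A prescription will be mandatory for infant patients from 6 to 12 months old".

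Prescription status is a Yes/No item in Table 2 (6.4), which the investigator completes at enrolment. The list headed "Variables to be collected in pre-screening log by the pharmacist" (6.4, with a parallel list in 6.9) holds age, reason for non-inclusion and reason for refusal; 6.10 adds gender. The investigator's screening log (6.4) holds age, reason for non-inclusion, approximate start of the cough and the PCQ score. Neither log has a field for prescription status.

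**The concern.** The lower age band of SO8 is the same band to which IC3 applies. In that band, the characteristic to be described is also a condition of entry. An outcome meant to show how the product is dispensed would return the eligibility rule.

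What is at stake is interpretation. The study is meant to supply real-life data for the clinical evaluation (3.1.3 and section 5). A table line showing that all infants received the syrup on prescription could be taken as observed practice, although any infant whose parent bought it without a prescription could not have entered the study.

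**Working it through.** The protocol gives no numerical expectation for SO8, so there is no stated figure to reproduce. The check is a conditional probability.

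**Inputs**
- q: the true share of purchases for infants of 6–12 months made on prescription. The documents do not give it; 0.1, 0.5 and 0.9 are assumed to cover a wide range.
- a: the probability of being enrolled for an infant with a prescription, any value above 0.
- Probability of being enrolled for an infant without a prescription: 0, from IC3.

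**Formula**

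P(prescription | enrolled, 6–12 months) = q·a / [q·a + (1 − q)·0] = 1.

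**Results** (a cancels, so take a = 1)
- q = 0.1: 0.1 / (0.1 + 0.9 × 0) = 100%
- q = 0.5: 0.5 / (0.5 + 0.5 × 0) = 100%
- q = 0.9: 0.9 / (0.9 + 0.1 × 0) = 100%

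The result does not move with q, so it carries no information about q. A value below 100% could come only from a breach of IC3 or a recording error, and would then measure compliance with the criterion. Section 7.1 also limits the full analysis set to children who met every selection criterion, so an infant enrolled in breach of IC3 would fall outside it.

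**Older group.** No criterion conditions on prescription status from 13 months, so that percentage is free to vary and remains informative for the enrolled population.

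**What the logs can add.** Let m be the enrolled infants (all with a prescription), k the logged infants whose reason for non-inclusion is lack of a prescription, and u the logged infants who declined or were excluded for another reason. For the u infants, prescription status is not recorded. Among enrolled and logged infants together, the share with a prescription then lies between m / (m + k + u) and (m + u) / (m + k + u). A single logged case (k ≥ 1) would show that the share is below 100%. The share itself is not identified, because the u infants cannot be allocated, and families who do not agree to be logged appear nowhere.

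**The case against.** The case for leaving SO8 alone has several parts.

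- *SO8 is descriptive.* Section 5.2 states no hypotheses, and 7.2 plans no tests and limits confidence intervals to the primary and safety outcomes. A reader might infer that a formal comparison of age groups is planned and biased. The text does not support that: SO8 describes two groups side by side. This stands, and it limits the consequence.
- *The age split isolates the constraint.* Because the cut coincides with IC3, the infants are kept apart from the older children and the older figure is not contaminated. This also stands. A reader might infer that SO8 as a whole is uninformative; only the infant cell is.
- *The log is not silent.* The pharmacist checks the eligibility criteria orally (6.10) and can enter a reason for non-inclusion with the child's age. It would be too strong to say that the planned data can reveal nothing about infants without a prescription. They may reveal some cases, but not a proportion.
- *The excluded group may be small.* Section 8.1.3 calls the product "an OTC medication that can be purchased from the pharmacy without a prescription", and one might infer that purchases for infants without a prescription are common. That sentence is general and does not mention the 6–12 month band. IC2 requires purchase in line with the recommendations for use, and the full instructions for use (Annex I) are not reproduced. How frequent such purchases are is unknown.
- *The SAP could add a note.* It could relabel the infant cell. It could not recover a prescription status that neither log collects, and the entry rule and data fields are fixed in the protocol.

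These points reduce the weight of the concern. None of them makes the infant figure an observation of dispensing.

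**Conclusion.** The point holds for one cell of one exploratory outcome. For eligible enrolled infants of 6–12 months, SO8 will show 100% with and 0% without a prescription by design, and so says nothing about actual dispensing at that age. The figure for 13 months to 6 years is unaffected, as are the primary outcome, the safety outcomes and the sample size. The impact is minor.

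The conclusion assumes that IC3 is applied as written and that SO8 is computed from enrolled children, the only ones for whom prescription status is recorded. It makes no assumption about how often infants are given the product without a prescription and takes no view on the prescription rule.

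**What to change.** **Minimum change.** In 5.1.3, 6.3.3 and the Synopsis, restrict SO8 to children aged 13 months to 6 years, and add a sentence saying that the infant figure is set by IC3 and is not an outcome. If an infant line is kept in the table, label it as a check on eligibility. The cost is one or two sentences and no new data.

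**If an infant figure is wanted.** Add a Yes/No prescription field to the pharmacist's pre-screening log and the investigator's screening log (6.4, 6.9). Complete it for every approached purchaser who agrees, including those who decline and those not included. Report the infant share among all approached purchasers separately from the enrolled set: logged and enrolled families come through different selection and should not be pooled without comment. The cost is one tick-box in each log. The drawback is that only families who agree to be logged are counted, so the number approached but not logged should be reported alongside if it is known.
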